10.2.2 Visit 1/Enrollment Visit/Baseline Visit (Study Day 0)

The following procedures will be completed at Visit 1:

1. Confirmation of subjects' eligibility and assessment of inclusion/exclusion criteria;
2. Randomization of patients who met the inclusion criteria;
3. Assessment of the skin condition around the catheter site.
4. Performing immediate dressing changes at all DVC insertion sites based on subjects' conditions at enrollment, using either the subject device 3M™ Tegaderm™ CHG I.V. Securement Dressing or the 3M™ Tegaderm™ Transparent Film Dressing as per randomization results, and following routine departmental nursing procedures;

The following data will be collected at the first visit:

1. Demographic information (height, weight, gender, age at consent);
2. Past medical history and allergic history, collected according to HIS records: Collection of medical and allergic history within the last 3 months related to the inclusion/exclusion criteria, including but not limited to diabetes, immune-related diseases, skin conditions, etc.;
3. Vital signs: Pulse, blood pressure, respiratory rate, body temperature;
4. Relevant laboratory tests, including blood routine examination: Red blood cell (RBC) count, white blood cell (WBC) count, neutrophil ratio, hemoglobin, platelets, C-reactive protein, etc.;

5. DVC type, site of insertion, duration, documentation of any post-puncture exudation, application of any other products such as gauze, hemostatic pads, etc.;
6. Documentation of skin conditions around the catheter site, scoring with reference to the standards for evaluating local skin irritation as listed in the appendix;
7. Medication use in relation to the trial, including mainly fat emulsions, heparin, blood transfusions and antimicrobial drugs;
8. Adverse events, device defects, complaints.

10.2.3 Follow-up visits (number of visits to be marked if there are multiple visits during each dressing change)

Since the expected use duration of the test/control product is a maximum of 7 days, there will be at least one visit on the seventh day into the trial (if catheterization duration is longer than 7 days), and more visits could be taken on a case-by-case basis. The following procedures will be completed at Follow-up visits:

1. Performing dressing changes in accordance with routine departmental nursing procedures;

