3.2 Study Population and Sample Size

440 subjects who meet the inclusion/exclusion criteria will be enrolled. Subjects will be adult voluntary clinical subjects, of either sex, at least 18 years of age, who are ICU patients undergoing deep venous catheterization (DVC), in which a CVC catheter must be used while other types of catheters such as hemodialysis, PICCO, and floating catheters may be used concurrently.

This study will use a positive two-sided Z test for continuity calibration and use the O'Brien-Fleming expenditure function to determine the test boundary. Assuming a baseline value of 18.7% for CVC tips colonization rate in the control group (this figure is reported by a domestic epidemiological survey) and a reduction rate of 50.0%, each group should contain at least 220 patients with CVC to reach an 80% likelihood at 5% significance level. A total of 440 valid cases are required in both groups combined. An interim analysis is scheduled for this study and will be conducted after completion of follow-up visits of 220 subjects to correct for the pre-defined sample size.

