6.2.2 General Information

- (1) Evaluation Indicators
 - 1) Demographic information: Age, gender, nationality, height and weight;
 - 2) General Condition: medical history, allergic history.
 - 3) Deep vein indwelling catheterization and peripheral skin evaluation status: Insertion site, insertion type, duration of insertion (days), with or without blood oozing after puncture placement, whether other products were applied, whether emergency insertion was performed, whether skin assessment around the insertion site was performed, skin assessment around the insertion site (including erythema, edema, pruritus score and whether skin infection was diagnosed);
 - ♦ Methodology for calculating relevant indicators:
 - ✓ Age (years) = (date of informed consent date of birth + 1) / 365.25, rouding to whole numbers
 - ✓ Duration of tube insertion (days) = date of randomization date of tube insertion + 1
- (2) Evaluation method

FAS was used for evaluation.

The demographic data, general conditions were described accordingly to their numerical characteristics and quantitative indicators were compared between the two groups of participants using t-test/Wilcoxon rank sum test; qualitative indicators were compared between the two groups of participants using chi-square test/Fisher exact probability method.

Summary of the evaluation of deep vein indwelling catheterization and surrounding skin at the level of the insertion site. The two groups of quantitative indicators were compared using t-test/Wilcoxon rank sum test according to their corresponding numerical characteristics description; and the two groups of qualitative indicators were compared using chi-square test/Fisher exact probability method.

In addition, a list of data on medical history, allergic history, deep vein indwelling catheterization prior to enrollment and skin evaluation around the insertion site, and previous/concomitant medication was made for both groups of participants.

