6.2.3.2 Pre-treatment and combined medication/treatment

Pre-treatment and combined medications were coded according to the classification of the Dictionary of Contemporary Drug Trade Names and Aliases (organized and edited by the Chinese Pharmaceutical Association, published and distributed by Chemical Industry Press and Modern Biotechnology and Pharmaceutical Technology Publishing Center, 2nd edition, August 2006). Pre-treatment medication is defined as medication prior to the first application of any investigational product. Combined medication was defined as any medication at and after the first application of investigational product. Pre-treatment and combined medications were summarized for each group according to the coded systemic and canonical names, and the number of cases, percentage, and case times were calculated. Details of pre-treatment and combined medications are given in list form.

Pre-treatment and combined treatments were coded according to the latest edition of the Medical Dictionary for Regulatory Activitie (MedDRA) classification. Pre-treatment is defined as treatment prior to the first application of any investigational product. Combination treatment was defined as any treatment at and after the first application of investigational product. The groups were summarized by system organ classification (SOC) and preferred terminology (PT), and the number of cases, percentage, and case times were calculated. Details of pre-treatment and combined treatment are given in list form.

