6.3 Efficacy Evaluation

6.3.1 Primary Efficacy Evaluation

(1) Evaluation Indicators

Occurrence rate of bacterial colonization of the CVC tip segment and skin at the insertion site after extubation (number of culture-positive cases/total catheters × 100%)

Primary endpoint: Positive rates of catheter tip cultures and sampling cultures of skin surrouding the insertion site in patients with deep vein indwelling catheterization after CVC tubes were removed.

(2) Evaluation method

FAS and PPS were used for both total catheter count and participant level evaluation. If more than one catheter of the same type was available for the same participant and the culture results were inconsistent, a positive culture result was taken for that participant when participant-level analysis was performed.

Describe the number and percentage of cases of bacterial colonization of the CVC tip segment and skin at the insertion site after extubation in both groups, and compare the two groups using a chi-square test or Fisher's exact test.

In addition, because some subject may have two or more than two CVC, which are interrelated, a generalized mixed linear model was developed to evaluate the difference in the occurrence rate of bacterial colonization between the two groups, using the occurrence rate of bacterial colonization of the CVC tip segment after extubation and the occurrence rate of bacterial colonization of the skin at the CVC insertion site after extubation as dependent variables, group as a fixed effect, and insertion site, skin infection of baseline insertion site, and their interaction as random effects, respectively.

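### Baseline antimicrobial use and emergency insertion are recorded but enter no efficacy analysis; the loss is modest, and a pre-specified adjusted model would recover it cheaply

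*SAP*

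**What the plan says.** **Collected.** Protocol 10.2.2 lists among the Visit 1 data "Medication use in relation to the trial, including mainly fat emulsions, heparin, blood transfusions and antimicrobial drugs", together with the site of insertion. SAP 6.2.2 adds to the baseline catheter description "whether emergency insertion was performed". That section counts insertion duration from tube insertion to randomisation, so the catheter is already in place and its emergency status is fixed before allocation.

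**Used.** SAP 6.2.2 describes the catheter items and compares them between arms by t, rank-sum, chi-square or Fisher tests. SAP 6.2.3.2 codes medications and summarises them by arm, then says: "Details of pre-treatment and combined medications are given in list form".

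**Efficacy.** SAP 6.3.1 compares colonization of the CVC tip and of the insertion-site skin by chi-square or Fisher test, at catheter and participant level. Because some subjects may have more than one CVC, it adds a generalized mixed model with "group as a fixed effect, and insertion site, skin infection of baseline insertion site, and their interaction as random effects, respectively". The catheter-day model in SAP 6.3.2 has the same structure. The other efficacy comparisons are unadjusted.

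**Randomisation.** SAP 3.3 gives a 1:1 ratio, names no stratification factor and refers to a separate randomisation scheme.

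**The concern.** A patient already on an antimicrobial may be less likely to yield a positive tip or skin culture, and a catheter placed in an emergency may be more likely to. If so, two things follow from leaving both out of the efficacy analyses.

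- Outcome variation that the trial already measures stays in the comparison and costs some precision.
- If chance leaves the arms unequal on one of these factors, the primary estimate moves and no correction is planned. SAP 6.2.2 tests some baseline differences but does not say what follows if one is found. In an open-label trial, an adjustment chosen after seeing the data would carry little weight.

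**Working it through.** **Inputs from the documents.** "Assuming a baseline value of 18.7% for CVC tips colonization rate in the control group"; "a reduction rate of 50.0%, each group should contain at least 220 patients with CVC"; "to reach an 80% likelihood at 5% significance level" (SAP 3.2). Hence 18.7% v 9.35%, a difference of 9.35 points. The final test is at two-sided 0.048 (SAP 6.1) and the interim test at 0.005 (SAP 8).

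**Assumed inputs.** The documents give no prevalence, strength or direction for any predictor. Everything below on antimicrobials, emergency insertion and site is assumed and shown as a range.

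**1. The plan's own figure.** n per group = [z(1−α/2)·√(2p̄q̄) + z(0.80)·√(p₁q₁+p₂q₂)]² / d², with p̄ = 0.14025 and d = 0.0935.
- √(2 × 0.14025 × 0.85975) = 0.4911; √(0.1520 + 0.0848) = 0.4866.
- α = 0.05: (1.960 × 0.4911 + 0.8416 × 0.4866)² / 0.008742 = 215.3, so 216.
- α = 0.048: the same with 1.977 gives 218.0, so 219.

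The stated 220 is reproduced, and power at 220 is 80.8% (0.05) or 80.4% (0.048). So 220 per group gives the planned power for an unadjusted test and does not rely on adjustment. (SAP 3.2 says "This study will use a positive two-sided Z test for continuity calibration". With a continuity correction 237 to 239 per group would be needed, which is a separate matter.)

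**2. Average power.** Simulated with 440 patients, one CVC each, overall rates held at 18.7% and 9.35%, and α = 0.048. The chi-square test is compared with a logistic model adjusting for all three factors.

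Set A: 60% on antimicrobials, 30% emergency insertions, three sites at 50/30/20%; 4,000 runs. Odds ratios for antimicrobials are the inverse of those shown.

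| Odds ratios (antimicrobial, emergency, extreme site contrast) | Unadjusted | Adjusted |
|---|---|---|
| 1, 1, 1 | 80.3% | 80.0% |
| 1.3, 1.3, 1.3 | 81.5% | 81.5% |
| 1.5, 1.5, 2 | 81.1% | 81.3% |
| 2, 2, 3 | 81.1% | 82.4% |
| 3, 3, 4 | 80.8% | 84.8% |

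Set B: 60% on antimicrobials, 30% at a higher-risk site, 25% emergency insertions; 10,000 runs. Missing outcomes are filled as positive, as in SAP 7.3. The missing fractions are assumed.

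| Odds ratios (antimicrobial, site, emergency) | Missing | Unadjusted | Adjusted |
|---|---|---|---|
| 0.4, 2, 2 | 0% | 80.4% | 82.7% |
| 0.4, 2, 2 | 10% | 55.4% | 56.6% |
| 0.4, 2, 2 | 20% | 38.6% | 39.1% |
| 0.25, 3, 2.5 | 0% | 80.6% | 85.2% |
| 0.25, 3, 2.5 | 10% | 55.4% | 57.9% |
| 0.25, 3, 2.5 | 20% | 38.8% | 40.0% |

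With no treatment effect, both tests rejected in about 4% to 6% of runs, consistent with the nominal 4.8%.

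**3. Chance imbalance in antimicrobial use.** At 60% use and 220 per arm, the SD of the between-arm difference is √(2 × 0.6 × 0.4 / 220) = 4.67 points. P(difference of 8 points or more) = 2 × P(Z > 8/4.67) = 8.7%. The shift in the risk difference is 0.08 × (risk in non-users − risk in users), with the average risk held at 14.0%:

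| Odds ratio | Non-users | Users | Shift |
|---|---|---|---|
| 0.67 | 17.0% | 12.0% | 0.4 points |
| 0.4 | 20.8% | 9.5% | 0.9 points |
| 0.25 | 24.1% | 7.3% | 1.3 points |

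For a 30% factor such as emergency insertion, the SD is 4.37 points and P(over 10 points) is about 2%. From a 12% base risk, a 10-point imbalance shifts the risk difference by 0.5 points (OR 1.5) to 1.7 points (OR 3).

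**4. Site as a random effect.** With three sites and site odds ratios of 2, 3 and 4 (600 runs each), random-site and fixed-site estimates of the group effect correlate at 0.998 or higher. Power is 82.7% v 81.5%, 81.3% v 80.8% and 84.3% v 84.2% (random v fixed).

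**5. Events available.** Final: 220 × (0.187 + 0.0935) = 61.7 positives. Interim: 110 × 0.2805 = 30.9. With three sites the model has five terms (group, two for site, antimicrobials, emergency), or about 12 events per term at the end and 6 at the interim.

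**The case against.** The strongest case against is that this is a preference and not a fault. Randomisation makes the chi-square test valid, 220 per group already gives about 80% power for it without continuity correction, and nothing in the documents shows that these factors predict colonization here. Exclusion criterion EC-3 removes patients judged at high risk of CLABSI, partly on site conditions, which may narrow the spread of risk. Imbalance would also be visible, since SAP 6.2.2 and 6.2.3.2 report these items by arm. All of this stands and limits the size of the point. It does not remove it: seeing an imbalance is not a plan for handling it.

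Three stronger readings are tempting and not supported.

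- **That the random site effect makes the adjustment unreliable.** With few sites the site variance is poorly estimated, but step 4 shows that the group effect and its power are essentially unchanged.
- **That the plan gives away material power.** Step 2 shows gains of 4 to 5 points only when all three factors are very strong, and smaller gains once missing outcomes are filled.
- **That randomisation is known to be unstratified.** SAP 3.3 defers to a scheme that is not among the documents.

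**Conclusion.** The point holds in a limited form. Two recorded, plausibly prognostic baseline items enter no efficacy analysis, and no correction for imbalance in them is planned. The unadjusted comparison remains valid.

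Under the assumptions shown, adjustment is worth about 0 to 2.5 points of power, 4 to 5 at the extreme, and about 0.5 to 2.5 in the scenarios run with 10% or 20% of outcomes missing and filled as positive. The more useful gain is protection in an unlucky draw. Roughly one trial in eleven would have an antimicrobial imbalance of 8 points or more, and at 8 points the shift is 0.4 to 1.3 points, or about 4% to 14% of the 9.35-point target. Adjustment costs essentially no power if the factors turn out not to matter. This merits a short SAP change; it is not a threat to the trial's conclusion.

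**What to change.** In SAP 6.3.1:

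- **Participant level.** Pre-specify a logistic model for CVC-tip colonization, and likewise for skin colonization, with group, insertion site, systemic antimicrobial use at randomisation (yes/no) and emergency insertion (yes/no) as fixed effects. Report the standardised risk difference and ratio. State in advance which CVC supplies the site and emergency status when a participant has several, and how sparse sites are merged.
- **Timing.** Use values from before randomisation only, and do not adjust for antimicrobials started later. SAP 6.2.3.2 splits medications at first product application, so the covariate needs its own definition by start date and time.
- **Catheter level.** Add the same covariates with a subject random effect or subject-clustered standard errors. The present model is justified by several CVCs within a subject but lists no subject term.
- **Governing test.** State which test is held to the 0.005 and 0.048 boundaries. If the chi-square test keeps that role, the adjusted model is the pre-specified supporting analysis.

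The cost is SAP wording and one or two models. No new data should be needed, provided that the case report form, which is not among the documents, records route and start time. The downside is a model-based estimate with limited events per term, especially at the interim with about 31 expected positives.

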3.0 STUDY DEVICE INFORMATION

Trial product

Working principle:

The primary purpose of 3M™ Tegaderm™ CHG I.V. Securement Dressing is to secure devices to skin; and secondly, the dressing contains an antimicrobial ingredient that inhibits microbial regeneration. This product is used to cover and protect the catheter sites on the body surface and to secure devices to skin and is available in a variety of models and sizes.

Product model: 1657R, 1658R, 1659R, 1660R

Size: 1657R, 8.5 cm x 11.5 cm (3-12 in x 4-1/2 in);

1658R, 10 cm x 12 cm (4 in x 4-3/4 in);

1659R, 10 cm x 15.5 cm (4 in x 6-1/8 in);

1660R, 7 cm x 8.5 cm (2 3/4 in. x 3 3/8 in)

The average CHG content (mg of CHG contained in the gel pad) of a single piece of dressing: 45 mg for both 1657R and 1658R; 78 mg for 1659R and 15 mg for 1660R.

Product usage

3M™ Tegaderm™ CHG Chlorhexidine Gluconate I.V. Securement Dressings is used to cover and protect catheter sites and to secure devices to skin.

Indications

The product is suitable for covering and protecting catheterization sites (covering arterial and venous catheters, intravascular catheters and percutaneous devices) on the body surface and securing the device to healthy skin. This product should not be used on infected wounds or unhealthy skins.

Contraindications

1. Do not use on patients with known hypersensitivity to chlorhexidine gluconate or alcohol;
2. Do not use at catheter insertion sites with dermatitis, burns, lesions or tattoos.

Warning

1. Use on infants with caution.
2. For external use only. Do not contact the product with ears, eyes, mouth or mucous membranes.

Precautions

1. The product shall not be used on broken wounds or unhealthy skin.
2. The product shall not be re-sterilized by gamma, electron beam or steam.
3. The skin must be dry and free of soap and hand sanitizer residue to prevent skin irritation and ensure good adhesion.

Possible adverse reactions associated with chlorhexidine gluconate

1. Occasionally, it can cause contact dermatitis. Highly concentrated solutions are highly

irritating to the eyes and conjunctiva.

2. Rare cases of local irritation and allergic reactions have been reported.
3. Children who accidentally eat it may develop symptoms of alcohol poisoning (e.g. slurred speech, drowsiness, wobbly gait, etc.) and there should be no delay in emergency medical treatment.

Control product

3M™ Tegaderm™ Transparent Film Dressing 1626W

Working principle

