7.0 ENROLLMENT CRITERIA

Subjects enrolled in this clinical study must meet all the inclusion criteria and none of the exclusion criteria, as listed in the sections below.

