7.1 Inclusion Criteria

Subjects may be included that meet the following criteria:

Table 7.1-1: Inclusion Criteria

| Number | Inclusion Criteria |
|--------|--|
| IC - 1 | The subject is 18 years old or older at the time of providing consent. |
| IC - 2 | The subject will be available to attend all visits required in the trial and have an expected length of stay in the ICU no less than 3 days. |
| IC - 3 | The subject or his/her legally authorized representative is competent to sign the informed consent form |
| IC - 4 | The patient must have a central venous catheter (CVC) used on him/her, which may or may not be used in combination with other types of DVCs |
| IC - 5 | The patient's catheter insertion site is free of deformities, phlebitis, infiltrations, dermatitis, eczema, rashes, breaks, burns, tattoos, or other skin conditions that could affect the integrity of the skin at the insertion site |
| IC - 6 | The patient will comply with the DVC treatment process and the nursing process prescribed in this protocol |

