7.2 Exclusion Criteria

Subjects must be excluded from participating in this study if they meet any of the following criteria:

Table 7.2-1: Exclusion Criteria

| Number | Exclusion Criteria |
|---------|--|
| EC - 1 | The subject is unwilling/unable to attend the study visits. (Different from IC) |
| EC - 2 | There is sunburn, skin infections or scars, moles or other blemishes on the subject's catheter site that would affect the scoring or measurement of the test site |
| EC - 3 | The patient is assessed by the investigator as being at high risk of CLABSI, or known to be CLABSI, based on the environment, duration, and site conditions of catheterization |
| EC - 4 | The patient is documented or known to have allergies (sensitivities) to adhesive products, or other products involved in the trial, e.g. transparent dressings, CHG and alcohol |
| EC - 5 | The patient is being or has been subjected to other antibiotic, catheter or skin-related clinical trials |
| EC - 6 | The patient needs topical application of creams containing antimicrobial ingredients or other antimicrobial fluids beneath the Tegaderm CHG dressing or transparent dressing for skin disinfection, in addition to the requirements of this protocol |
| EC - 7 | The patient is assessed by the investigator as being at high risk of blood stream infection, or known to be sepsis, caused by blood stream infection |
| EC - 8 | The patient has dermatitis, burns, lesions, breaks, eczema, tattoos or other conditions at the catheter insertion site that would interfere with observation in the trial |
| EC - 9 | Women who are pregnant or breastfeeding |
| EC - 10 | Other patients deemed unsuitable for this trial by the investigator's judgment |

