6.3.2 Secondary Efficacy Evaluation

- (1) Evaluation Indicators
 - Number of positive cases per 1,000 catheter-days of bacterial colonization at CVC tips;
 - 2) Bacterial colonization rate at the tip of other types of (percutaneous) deep vein

catheters and the catheterization site (number of culture positive cases/total catheters x 100% and number of positive cases per 1,000 catheter-days), including hemodialysis, PICCO, float catheters, etc;

- 3) Occurrence of suspected CLABSI/CRBSI, which entails catheter tip bacterial culture and blood bacterial culture
- 4) Securement performance of the dressing: Frequency of dressing changes associated with wearing time and warping or peeling
- (2) Evaluation method

FAS and PPS were used for evaluation.

Quantitative descriptive statistics (number of cases, mean, standard deviation, median, minimum, maximum) were used to describe the number of positive cases per 1,000 catheter-days occurring in the two groups of CVC tip bacterial colonization, and t-test or rank sum test was used to compare the two groups. In addition, a mixed linear model was developed to evaluate the difference in the number of positive cases per 1,000 catheter days of bacterial colonization between the two groups, using the number of positive cases per 1,000 catheter days of bacterial colonization of the CVC tip segment after extubation as the dependent variable, group as a fixed effect, and insertion site, skin infection of baseline at the insertion site, and their interaction as random effects.

The number and percentage of cases of bacterial colonization at the tip of other types of (percutaneous) deep vein catheters and the catheterization site after extubation were described separately for both groups with the total number of catheters and at the participant level, and the two groups were compared using the chi-square test or Fisher's exact test.

Quantitative descriptive statistics (number of cases, mean, standard deviation, median, minimum, maximum) were used to describe the number of positive cases per 1,000 catheter days occurring at the tip of other types of (percutaneous) deep vein catheters and the catheterization site after extubation in both groups. If more than one catheter of the same type was placed in the same participant, it will be analyzed with the total number of catheters and participant level separately and the two groups will be compared using a t-test or Wilcoxon rank sum test.

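### SAP 6.3.1 and 6.3.2 put baseline skin infection, and its interaction with insertion site, in the mixed models as random effects, although the entry criteria leave that variable essentially constant

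*SAP*

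**What the plan says.** SAP 6.3.1 compares tip colonization and skin colonization between groups by chi-square or Fisher's exact test. It then adds a generalized mixed model for each outcome, on the ground that a subject may have two or more CVCs whose results are related. Group is the fixed effect. The random effects are "insertion site, skin infection of baseline insertion site, and their interaction as random effects, respectively".

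SAP 6.3.2 uses the same structure in a linear mixed model for tip colonization per 1,000 catheter-days, supplementing a t-test or rank-sum test. The random effects are again "insertion site, skin infection of baseline at the insertion site, and their interaction as random effects".

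SAP 6.2.2 shows where the covariate comes from: the baseline skin assessment records whether a skin infection was diagnosed. Protocol 10.2.2 places that assessment at Visit 1, where eligibility is also confirmed.

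On eligibility, Protocol 7.2 (EC-2) excludes a subject if "There is sunburn, skin infections or scars, moles or other blemishes on the subject's catheter site that would affect the scoring or measurement". Protocol 7.1 (IC-5) requires a site free of a list of conditions and of "other skin conditions that could affect the integrity of the skin at the insertion site". Protocol 7.0 makes the criteria binding: "Subjects enrolled in this clinical study must meet all the inclusion criteria and none of the exclusion criteria". For the test dressing, Protocol 3.0 adds: "This product should not be used on infected wounds or unhealthy skins".

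**The concern.** A random effect is useful only if its grouping factor has several levels with data in each. Here the entry criteria remove nearly everyone who could occupy the 'yes' level of baseline infection. The factor then has one populated level, and crossing it with insertion site gives back insertion site.

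What is at stake is pre-specification. A model with redundant variance components tends to return zeros, non-unique values or a convergence failure. Someone must then decide which terms to drop. In an open-label trial that decision should not be left until results are being produced. It matters a little more in SAP 6.3.1, because this model is the only catheter-level analysis of the primary endpoint that is meant to handle several CVCs in one subject.

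**Working it through.** The documents give no figure for these terms, so there is nothing to reproduce. The check has three steps.

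**1. Can the variable vary?**

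| Source | What it does to 'baseline skin infection = yes' |
|---|---|
| Protocol 7.2, EC-2 | Excludes it where it would affect scoring or measurement of the site |
| Protocol 7.1, IC-5 | Does not name infection, but excludes conditions that could affect skin integrity |
| Protocol 7.0 | Makes both criteria binding |
| Protocol 3.0, test dressing | Not for infected wounds or unhealthy skin |
| Protocol 3.0, control dressing | Mixed: a warning against infected catheter sites, and a precaution allowing infected areas under professional care |
| Protocol 10.2.2 and SAP 6.1 | Eligibility and the baseline skin assessment fall at the same visit; baseline is the last value before treatment |
| Protocol Appendix A | Version 2 changed only EC-3 and EC-7, so EC-2 is the same under version 1.0, which the SAP cites |

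The two control-dressing statements need reconciling, and I place no weight on them. The other rows are enough: if the criteria are followed, the expected number of infected CVC sites at baseline is close to zero.

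**2. What happens to the model?** Write the linear predictor for CVC *i* at site *s* with infection status *f* as

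η = β₀ + β₁·group + a(s) + b(f) + c(s,f),

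with variances σ²_site, σ²_inf and σ²_int. If every CVC has *f* = no, this becomes

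η = (β₀ + b(no)) + β₁·group + [a(s) + c(s,no)].

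- b(no) is a single draw shared by all CVCs, so it cannot be separated from β₀.
- a(s) and c(s,no) have the same levels. Their sum has variance σ²_site + σ²_int, and only that sum enters the likelihood.

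In the linear model of 6.3.2 the identifiable components are therefore that sum and the residual, 2 of 4. In the generalized model of 6.3.1, which has no separate residual variance, it is 1 of 3.

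**3. Numerical check.** Assumptions, not taken from the documents: one CVC for each of the 440 subjects, three insertion sites split 50/35/15%, and *k* infected sites. For each random term I formed its covariance matrix, projected out intercept and group, and took the rank of the set of variance components including the residual.

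| *k* | Levels of site / infection / interaction | Identifiable components (of 4) |
|---|---|---|
| 0 | 3 / 1 / 3 | 2 |
| 1 | 3 / 2 / 4 | 4 (formal) |
| 2 | 3 / 2 / 4, or 5 if the two are at different sites | 4 (formal) |

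At *k* = 0 the projected infection matrix is exactly zero, and the site and interaction matrices are identical. At *k* = 1 or 2 the rank is full, but the 'yes' level of infection holds one or two CVCs out of 440 and the interaction adds only one or two cells. A variance cannot be usefully estimated from that.

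**Effect on the group estimate.** At *k* = 0 the redundant terms do not change the mean structure for group. The infection term is absorbed by the intercept, and splitting one variance into two does not alter their sum. In a simulation at the planning rates, with modest assumed site differences, treating site as fixed rather than random moved the log odds ratio for group by about 0.01. The planned effect, 18.7% against 18.7% × 0.5 = 9.35%, is ln(0.0935/0.9065) − ln(0.187/0.813) = −2.27 + 1.47 ≈ −0.80.

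**The case against.** The strongest reply has three parts.

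- **These are supplementary models.** This stands. Both sections introduce them in addition to simpler tests, and Protocol 19.4 names only chi-square or Fisher's test for tip colonization. If the software sets the redundant variances to zero, the group comparison is essentially unharmed. A reader might infer that the treatment effect is biased or the primary comparison invalid. The documents do not support that: the chi-square/Fisher comparison does not use these terms, and no bias, error inflation or loss of power follows from them.

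- **Eligibility does not force the variable to be constant.** This stands in part. EC-2 applies only to infections that would affect scoring or measurement, and IC-5 does not name infection. The FAS can also keep subjects who entered in breach of the criteria, and the SAP does collect the item. It is therefore too strong to say that no infected site can occur, or that the redundancy is exact in every case; it is exact only at zero infected sites. A handful of cases makes the terms estimable in form only.

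- **Deleting terms may remove what the model is for.** This is a fair warning. The stated purpose is several CVCs per subject, yet no subject term is listed. Dropping infection and making site fixed, with nothing else, would leave an ordinary regression that treats CVCs from one subject as independent. The correction has to supply the subject-level term.

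A reader might also infer that leaving out antimicrobial use at enrolment is an error. Protocol 10.2.2 lists antimicrobial drugs among the medication recorded at Visit 1, but gives neither route nor prevalence. Use could be near universal in an ICU, and a randomized comparison does not require the covariate.

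**Conclusion.** The point holds, at minor severity. Two of the three random terms in SAP 6.3.1 and 6.3.2 are redundant if no eligible CVC site is infected at baseline, and nearly uninformative if one or two are. The likely result is zero or non-unique variance components or non-convergence, and hence a post hoc choice of model in an open-label trial. The group estimate should change little.

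This rests on the entry criteria being broadly followed. That baseline infection will be close to absent is an inference from those criteria, since the documents give no count. The three-site split affects only the level counts in the table; the confounding at zero infected sites does not depend on it. The SAP models themselves were not fitted to data, so the software behaviour is expected, not shown.

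**What to change.** In SAP 6.3.1 and 6.3.2:

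1. Delete baseline skin infection and its interaction with insertion site from the random effects.
2. Enter CVC insertion site as a fixed categorical effect alongside group.
3. Add a subject-level random intercept, or specify a GEE clustered on subject, and state in advance which one applies. Protocol 10.2.4 records only the first removal of each catheter type when a catheter is replaced, so subjects with more than one CVC may be few and a random-intercept variance may itself be weakly estimated. If the random intercept is chosen, name the GEE as the fallback for non-convergence.
4. Keep baseline skin infection as an eligibility check and in the listing.

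Optionally, pre-specify antimicrobial use at enrolment as a fixed covariate, provided that data pooled over groups, reviewed blind to allocation, show that it varies. The core change does not depend on this.

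The cost is SAP wording and one or two extra fixed-effect parameters. No new data are needed.
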